# 32.2 Routine Study Termination and Close Out

Routine close-out procedures will be conducted ensuring that the PI's records are complete, all documents needed for the sponsor files are retrieved, remaining clinical investigation materials are disposed of, previously identified issues have been resolved.

### 33. Data Management Procedures

The investigator will prepare and maintain adequate and accurate source documents designed to record all observations and other pertinent data for each enrolled subject. Study Staff at each site will enter data from source documents corresponding to a subject into the protocol- specific Case Report Form. Subjects shall not be identified by name in the study database or on any study documents but will be identified by a site subject number. The handling of all data on the Case Report Form will be the responsibility of the PI.

The de-identified data will be entered into a validated database. Once all the quality assurance steps have been completed and the data integrity verified the database shall be locked. Analysis of these anonymized data will be conducted according to a pre-determined statistical analysis plan.

Vestibular Stimulation to Trigger Adip Clinical Trial Project Name	91 of 112
Clinical Protocol for VeS	
243973(NI)_181094(UCSD USA) Study Reference Number	11 Revision Number

Data from subjects who received treatment, who withdraw voluntarily or who are withdrawn from the clinical investigation, will be used in the final analysis. The inclusion of partial data will be documented in the final report.

All procedures for the handling and analysis of data will be conducted using good computing practices meeting FDA guidelines for the handling and analysis of data for clinical trials.

## 33.1 Data Archiving

The database is safeguarded against unauthorized access by established security procedures; appropriate backup copies of the database and related software files will be maintained. Databases are backed up by the database administrator in conjunction with any updates or changes to the database.

At critical junctures of the protocol (e.g., production of final reports), data for analysis is locked and cleaned per established procedures.

### 34. Statistical Plan

Prior to analysis of the final study data a detailed statistical analysis plan will be written describing all analyses that will be performed.

### 34.1 Statistical Plan

#### Analysis Populations

The Primary Analysis population will be the 200 subjects included in the study. The primary analysis population is defined to include all randomized subjects (i.e. an intention-to-treat population).

#### Representativeness Analysis

To evaluate the representativeness of the population the following analysis will be conducted on the:

### Primary Analysis Population:

As per the guidance from the FDA relating to the representativeness of the study population (https://www.fda.gov/downloads/MedicalDevices/DeviceRegulationandGuidance/GuidanceDocuments/UCM5 07278.pdf.source=govdelivery&utm\_medium=email&utm\_source=govdelivery) the following analyses will be conducted:

Vestibular Stimulation to Trigger Clinical Tria	92 of 112
243973(NI)_181094(U USA) Study Reference Number	11 Revision Number

For each demographic characteristic an appropriate statistical test will be conducted to flag any differences between the two respective subgroups (active and sham devices). For categorical data either a Chi-square test (if  $n \ge 5$  in each table cell) or Fisher's exact test (if n < 5 in any single table cell), will be used, and for continuous a 2-sample t-test will be used to compare the respective subgroups.

Missing data will be clearly reported and included in tables, tests for representativeness will be conducted only on the data actually present.

### **Randomization**

Treatment assignments, investigation or sham devices will be generated via a randomized procedure, with participants randomly chosen in the permuted blocks. At baseline subjects will be assigned 1:1 between the treatment (investigational device) and control groups (sham device). Stratification will be performed by gender and center.

### Methods: Primary Aims

For total body weight loss (TBWL) as a continuous measure, we will use a linear regression with TBWL at each time period as the dependent variable and group and other covariates of interest (baseline total body weight, gender, age, study site) as independent variables. As a supportive analysis, we will also a two-sample t-test to examine the differences between the control and active treatment groups at each time period. To assess any longitudinal effects, we will use a linear mixed effects model for weight over time, with fixed covariates for baseline weight, time, group, and a time / group interaction, and a random intercept to account for within-subject correlation. We will use these models to generate two-sided 95% confidence intervals for the difference in mean percent weight loss.

We will calculate exact binomial confidence intervals (95%, two-sided) to determine if the response rate in the treatment group significantly exceeds 50%, with response defined by a loss of at least 5% of their body weight at the 6-month follow-up. As supportive analyses we will also use Fisher's exact test to compare the response rates in each group, and, will consider the use of a logistic regression to control for any other covariates of interest. To investigate possible longitudinal trends, we will fit a logistic mixed effects model, similar to the linear mixed effects model described above.

### Methods: Secondary Aims

Vestibular Stimulation to Trigger Adip Clinical Trial Project Name	93 of 112
Clinical Protocol for VeS	
243973(NI)_181094(UCSD USA) Study Reference Number	11 Revision Number

For each continuous and categorical variable at each time point, we will use a two-sample t-test and Fisher's exact test, respectively. Summary statistics (mean, standard deviation, quantiles, counts, and percentages) and plots will be produced for all demographic and study outcomes. We will investigate the effectiveness of the device by usage by including usage time as a continuous covariate in a linear model for total fat loss. Statistical personnel will conduct all analyses using the latest version of R (R Foundation for Statistical Computing, Vienna, Austria. http://www.R-project.org/).

We will analyze mean fat loss in the same way as TBWL as a continuous measure with t-tests, linear regression and linear mixed effects models.

### Missing Data

The primary hypotheses will be tested on the intent-to-treat population. Missing data will be clearly reported and included in tables. We will assess the assumption that the data is missing completely at random. For the primary effectiveness analysis of total body weight loss (TBWL) as a continuous measure we will perform a multiple imputation analysis. We will include the same covariates in the multiple imputation model as in the linear regression, i.e. group, baseline total body weight, gender, age, study site. Two supportive sensitivity analyses with different approaches to imputing missing data will also be performed: last observation carried forward (LOCF) and baseline value carried forward (ie assuming no weight loss).

A sensitivity analysis will be performed with the binary weight loss endpoint. This analysis will include a bestcase scenario (assuming subjects with missing values have all lost over 5% body weight), a worst-case scenario (assuming no subjects with missing values have lost over 5% body weight), and a tipping point analysis (as described in Yan et al., 2009).

#### Interim Analysis

There is no planned interim analysis.

### 34.2 *Primary Endpoints USA Regulatory Clearance:*

The efficacy of the VeSTAL device within the treatment group will be quantified by calculation of two primary endpoints after 6 months treatment:

- mean percent weight loss;
- proportion of participants who lose at least 5% body weight.

Vestibular Stimulation to Trigger Adipose Loss (VeSTAL) Clinical Trial			
Clinical Protocol for VeSTAL			
243973(NI)_181094(UCSD USA) Protocol 01			
	TAL	TAL Protocol 01	

## Study Acceptance Criteria USA:

- Mean: There should be at least a 2% total body weight loss (TBWL) superiority margin between the active-product and sham-treated groups.
- Categorical: The proportion of participants who lose 5% TBWL or more in the active-product group is at least 50%, independent of the sham control

### Primary Outcome Measures USA (6 months)

- Mean: There should be at least a 2% total body weight loss (TBWL) superiority margin between the active-product and sham-treated groups.
- Categorical: The proportion of participants who lose 5% TBWL or more in the activeproduct group is at least 50%, independent of the sham control.

Both weight loss efficacy acceptance criteria must be met to claim success. These criteria can be specified in mathematical formulae as follows:

Rejection of both the null hypotheses  $\mu A - \mu C \le 2\%$  and  $\pi A \le 50\%$  at the 2.5% (1-sided) level Where:

 $\mu A$  and  $\mu C$  are the underlying population mean percentage weight loss on active and control respectively

 $\pi A$  is the underlying population proportion of subjects who lose  $\geq 5\%$  of baseline body weight on active.

## Secondary Endpoints USA

A variety of secondary endpoints will also be assessed statistically at the 6-month timepoint after the primary endpoints. The following of these may form the basis of potential future labelling claims:

- Total body fat loss (as measured by whole body DXA scanning);
- Healthy Eating Index (HEI) score (https://epi.grants.cancer.gov/hei/) (as measured by the two-day 24-hour dietary recall);
- Total caloric intake (as measured by the two-day 24-hour dietary recall);
- Systemic inflammation (as measured by high-sensitivity C-reactive protein);

Vestibular Stimulation to Trigger Adip Clinical Trial Project Name	95 of 112		
Clinical Protocol for VeS			
243973(NI)_181094(UCSD USA)	11		
Study Reference Number	Document Type	Document Number	Revision Number

- Atherogenic index (as determined by the ratio of total cholesterol to HDL);
- Quality of life (as measured by the IWQoL questionnaire).

The full details of the testing procedures procedure for these endpoints will be laid out in the Statistical Analysis Plan. All other secondary endpoints at the 6-month timepoint will be hypothesis generating only.

### Secondary Outcome Measures USA (At 6 months)

- The difference in mean fat mass loss (in grams) between the active-product and shamtreated groups is statistically significant. (As measured by means of a whole body DXA scan).
- The difference in mean trunk fat loss (in grams) between the active-product and shamtreated groups is statistically significant. (As measured by means of a whole body DXA scan).
- The difference in mean visceral adipose tissue (VAT) mass loss (in grams) between the active-produce and sham-treated groups is statistically significant. (As measured by the whole body DXA scan).
- Difference in mean lean mass gain (in grams) between the active-product and shamtreated groups is statistically significant. (As measured by means of a whole body DXA scan).
- Difference in mean bone mineral content (BMC) gain (in grams) between the activeproduct and sham-treated groups is statistically significant. (As measured by means of a whole body DXA scan).
- Fasting glucose
- Lipid profile (Assess total non-HDL cholesterol, and HDL to total cholesterol ratio)
- High-sensitivity C-reactive protein
- Glycated hemoglobin (HbA1c)
- Two-day 24-hour dietary recall
- Modifiable activity questionnaire
- Blood pressure
- Heart rate
- Waist and hip circumferences (This will only be performed at the USA sites.)
- Body Mass Index (BMI)
- Quality of life IWQOL-Lite questionnaire.

Vestibular Stimulation to Trigger Adipose Loss (VeSTAL) Clinical Trial				96 of 112
Clinical Protocol for VeSTAL				
2	Document Title 43973(NI) 181094(UCSD			
U	ISA) udv Reference Number		01 Document Number	11 Revision Number

- Dose response analysis: it is likely that some subjects will not utilize their device for the mandated 7 hours per week. Usage data will be available from the devices permitting a dose response analysis, which will done be in an intention to treat manner.
- Adjustment of medication both reduction and new medications.
- Mentor support group usage (total hours).

# 34.3 *Primary Endpoints EU Regulatory Clearance:*

The efficacy of the VeSTAL device within the treatment group will be quantified by calculation of one endpoint:

1. Mean percent weight loss

## Study Acceptance Criterion EU:

1. Mean: There should be at least a 2% total body weight loss (TBWL) superiority margin between the active-product and sham-treated groups.

### Primary Outcome Measure EU (At 6 months)

1. Mean: There should be at least a 2% total body weight loss (TBWL) superiority margin between the active-product and sham-treated groups.

This criterion can be specified in formulae as follows:

 $mA - mC \ge 2\%$  and  $pt \le 0.05$ 

Where:

mA and mC are the observed mean percentage weight loss on active and control respectively pt is the p-value (two-sided) from a linear regression comparing percentage weight loss between active and control (H0:  $\mu$ A =  $\mu$ C; H1:  $\mu$ A  $\neq \mu$ C)

 $\mu A$  and  $\mu C$  are the underlying population mean percentage weight loss on active and control respectively

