	$\mu A$ and $\mu C$ are the underlying population mean percentage weight loss on active and control respectively
	This single study efficacy acceptance criterion for the EU regulatory clearance pathway will be treated to the same statistical analysis as the mean criterion for the USA regulatory clearance pathway.
Rationale for Number of Subjects	The primary outcomes are TBWL from the start of treatment (as a percentage of baseline total body weight), and the proportion of subjects who lose at least 5% of their baseline total body weight. These outcomes will be assessed at 6-months.
	
 
Power calculations are based on simulation with assumptions informed by pilot data and the Modius weight-loss device as follows:
 
90kg median baseline weight in both groups (log-normal distribution with CV=24%)
 
6.6% mean percent weight loss in the active group at 6 months (SD 3.9%),
 

Vestibular Stimulation to Trigger Adipose Loss (VeSTAL) Clinical Trial			21 of 112
Clinical Protocol for VeSTAL			
243973(NI)_181094(UCSI USA)	11 Pavision Number		
Study Reference Number	Document Type	Document Number	Revision Number

	
 
3.1% mean percent weight loss in the control group at 6 months (SD 3.9%),
 
correlation between baseline weight and weight loss at 6 months of -0.4.
 
	
	Under these assumptions, with a sample size of 180 participants randomized 1:1 active: placebo, there is greater than 80% power to demonstrate both the weight loss mean and categorical acceptance criteria at the 6 month timepoint.	

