# Neurovalens Limited Identifier: EXP18020

Clinical Study Identifier: 243973

For the purpose of the *EU regulatory clearance pathway*, the study will be deemed to have met the efficacy criteria if the hypothesis is rejected, and the following numerical criterion is achieved:

• The difference between the mean percentage weight loss of participants using the VeSTAL device and the sham control is at least 2% as observed from the mean estimates.

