## 12.1.1 Primary Efficacy Analyses

As the primary efficacy endpoints differ between regulatory clearance pathways, the primary efficacy analyses also differ accordingly.

For both the *EU and USA regulatory clearance pathways*, the primary efficacy endpoint will be summarized using summary statistics for the percentage weight loss at the 6 month time point. The mean percentage weight loss will also be presented graphically, by treatment group, over time. Summaries and graphical outputs will be produced for observed data unless specified otherwise..

For the continuous efficacy endpoint, mean percentage weight loss at 6 months, the difference between treatment groups will be assessed using a linear model controlling for covariates of interest: gender and baseline weight. The least square (LS) mean difference between groups will be assessed for a statistically significantly difference from 0 i.e. p-value <0.05. For the USA regulatory clearance pathway, the lower limit of the confidence interval of the LS Mean difference between groups will be assessed against the 2% target for a successful study, whereas the EU regulatory clearance pathway will assess whether the LS mean difference between groups is significantly different from zero. Analysis using multiple imputation for missing data will be primary, with the LOCF and BOCF imputation methods used for supportive analyses.

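### The EU criterion is worded as a 2% superiority margin, but its rule shows only superiority to sham with an observed difference of at least 2 points, and SAP 12.1.1 omits the 2 points

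*Protocol*

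**What the plan says.** **EU, protocol.** The Synopsis, 18.2 and 34.3 give the criterion in words: "Mean: There should be at least a 2% total body weight loss (TBWL) superiority margin between the active-product and sham-treated groups". The formula follows in each place: mA − mC of at least 2% and pt of at most 0.05. Here "mA and mC are the observed mean percentage weight loss on active and control respectively" and "pt is the p-value (two-sided) from a linear regression comparing percentage weight loss between active and control", with equal population means as the null.

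**USA, protocol.** The Synopsis, 18.1 and 34.2 use the same sentence for the mean criterion. There it is defined as "Rejection of both the null hypotheses", one of which is μA − μC ≤ 2%, at the one-sided 2.5% level.

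**SAP 2.3.1.** For the EU, the no-difference hypothesis must be rejected and the difference must be one that "is at least 2% as observed from the mean estimates". For the USA, the 2% is judged from the confidence interval.

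**SAP 12.1.1.** For the USA, the lower confidence limit is set against 2%. For the EU, "the EU regulatory clearance pathway will assess whether the LS mean difference between groups is significantly different from zero"; the 2% does not appear.

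**Synopsis, closing sentence of the EU pathway.** The EU criterion "will be treated to the same statistical analysis as the mean criterion for the USA regulatory clearance pathway".

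**The concern.** The phrase superiority margin has a settled meaning: the data exclude a true advantage at or below the margin. The USA definition has that property and the EU definition does not, although the same sentence introduces both. Someone who reads the words and then sees that the EU criterion was met could conclude that a 2-point advantage had been demonstrated, when the interval may reach below 1.

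The two pathways can also split on the same data. An observed difference between 2.0 and roughly 3.0–3.1 passes the EU rule and fails the USA mean rule.

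A second problem could change the verdict itself. Under SAP 2.3.1 and the protocol, an EU pass needs an estimate of at least 2 points. Under SAP 12.1.1 as written, significance against zero is enough. Both sections are current text in one document, so the SAP's statement in section 13 that its analyses supersede the protocol's does not settle which applies.

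**Working it through.** **Inputs** (protocol 34.3, Power Calculation; SAP 5): mean loss 6.6% active and 3.1% sham, so a planned difference of 3.5; SD 3.9 in both arms; correlation with baseline weight 0.4 in size (the two documents print opposite signs, which does not affect the residual SD); 180 participants, 90 per arm.

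**The plan's own figure.** The documents give no EU power. They state more than 80% for meeting both USA criteria.
- USA mean criterion alone: Φ(1.5/0.533 − 1.96) = 80.4% baseline-adjusted; Φ(1.5/0.581 − 1.96) = 73.2% unadjusted.
- USA categorical criterion alone: at least 55 responders of 90, with response probability Φ(1.6/3.9) = 0.659, gives 85.8%.
- Both together, by simulation at one-sided 2.5%: about 73%. The joint figure is not reproduced. That is a USA matter and does not bear on this point.

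**Standard error of the difference.**
- Adjusted: 3.9 × √(1 − 0.4²) × √(2/90) = 3.574 × 0.149 = 0.533.
- Unadjusted: 3.9 × √(2/90) = 0.581.

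**Which EU condition binds?** Significance against zero needs an observed difference of 1.96 × 0.533 = 1.04 (adjusted) or 1.96 × 0.581 = 1.14 (unadjusted). Both are below 2, so the p-value condition adds nothing once 2.0 is observed. This holds while 1.96 × SE < 2, which at 90 per arm means any SD up to about 6.8.

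**Pass probabilities at true difference d.** EU rule: 1 − Φ((2 − d)/SE). USA mean rule: 1 − Φ((2 + 1.96 × SE − d)/SE). Each range runs between the adjusted and unadjusted SE.

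| True difference | EU rule | USA mean rule |
|---|---|---|
| 0 | 0.01–0.03% | about 0 |
| 1.0 | 3.0–4.3% | about 0.01% |
| 1.5 | 17–19% | 0.2% |
| 2.0 | 50% | 2.5% |
| 3.5 (planned) | 99.5–99.8% | 73–80% |

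A simulation of 20,000 trials gave 50.0–50.3% for the EU rule at 2.0 and 3.0–4.1% at 1.0. With 100 per arm the EU figures are 16–18% at 1.5 and 2.4–3.5% at 1.0; the 50% does not move.

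**Interval at an observed 2.0.**
- Adjusted: 2 ± 1.04 = 0.96 to 3.04 (0.95 to 3.05 with a t multiplier of 1.97).
- Unadjusted: 2 ± 1.14 = 0.86 to 3.14.
- To exclude 2, the observed difference must exceed about 3.04 (adjusted) or 3.14 (unadjusted).

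**What the SAP conflict is worth.** If only significance against zero is required, the pass probability at a true difference of 1.0 is Φ((1.0 − 1.044)/0.533) = 47% adjusted, or Φ((1.0 − 1.140)/0.581) = 41% unadjusted. With the 2-point condition it is 3–4%.

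**The case against.** The strongest reply is that nothing is hidden. The formula comes straight after the sentence and defines its means as observed. SAP 2.3.1 contrasts mean estimates for the EU with confidence intervals for the USA, and SAP 1 says that the criteria differ by pathway. All of that stands: the EU rule is openly stated and deliberately different. What remains is that the words above it describe a property it lacks.

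Four stronger readings are tempting and are not supported:
- **A 50% type I error rate.** The EU rule's stated null is zero, and false success there is under 0.04%. At a true difference of exactly 2.0 the words at least 2% are true, and a pass rate near one half at the threshold is what any point-estimate rule gives. The 50% measures how little a pass says about a margin; it is not a loss of error control.
- **A direct contradiction in the Synopsis.** The sentence about the same statistical analysis is loose. It reads most naturally as the shared regression, which SAP 12.1.1 confirms is one linear model for both pathways.
- **A margin that is never examined.** The protocol plans 95% intervals for the difference, and SAP 12.1.1 sets the lower limit against 2% for the USA on the same data. The limit will exist; nothing ties it to the EU verdict.
- **A certain misreport.** No section says how an EU pass will be described, beyond the efficacy criteria having been met. The risk comes from the wording and is not a stated intention.

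**Conclusion.** The point holds as a mismatch between words and rule, together with an inconsistency inside the SAP. An EU pass supports superiority to sham with an estimate of at least 2 points; it can occur with a lower 95% limit below 1. That the rule does not demonstrate a margin follows from its form and needs no assumption. The pass rates and intervals rest on the plan's SD of 3.9 and 90 per arm with approximately normal estimates; the adjusted figures also use the 0.4 correlation. Any extra variance from multiple imputation is ignored.

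The omission in SAP 12.1.1 is the part that can change a decision. Read literally, it lowers the observed difference needed for an EU pass from 2.0 to about 1.04–1.14.

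**What to change.** Before unblinding:
1. In the Synopsis, protocol 18.2 and 34.3 (both the acceptance criterion and the outcome measure), reword the EU criterion to: VeSTAL is statistically superior to sham (two-sided p ≤ 0.05) with an estimated difference of at least 2 percentage points.
2. Add the 2-point condition to the EU rule in SAP 12.1.1 so that it agrees with SAP 2.3.1. In both sections, name the estimate: the LS mean difference from the primary multiple-imputation model.
3. State that an EU pass does not support a claim of a 2% margin unless the lower 95% limit exceeds 2%, and report that limit beside the EU verdict.
4. Narrow the Synopsis sentence to say that the EU criterion uses the same regression model as the USA mean criterion.

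The cost is a slightly less favourable EU claim, with no change to data or sample size. If the sponsor prefers to keep the margin wording, the rule would have to become the USA one. The pass probability at the planned 3.5 would then fall from 99.8% to 80.4% (baseline-adjusted).
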